19.1.3 Health Economics Analysis

The material used and nursing time spend to treat subjects with fecal or double incontinence over a three week (or shorter) period will be analyzed using an appropriate regression model. Detailed will be provided in the SAP.

19.2 Sample Size Justification

From a pilot study, the standard deviation of the percent change from baseline was estimated at 70%. A sample size of 51 patients per treatment group has at least 80% power to detect a mean difference of 45% change from baseline. The hypotheses tested will be:

 $H_0: \mu_T = \mu_C = 0$ versus $H_A: \mu_T \neq \mu_C$, where the subscript T = the investigational product and C = Control, the paste product.

19.3 Interim Analyses and Criteria for Termination of the Study

Also, one interim analysis will be done after half of the subjects are enrolled. The P-value for this analysis will be adjusted using an O'Brien-Fleming method, and will be considered significant at P <0.0056. Data from this interim analysis will be used to re-estimate the sample size, based on the primary analysis. To minimize bias, the study personnel will remain blinded to the results. The result for the analysis after all subjects are complete will be considered significant at P <0.0483

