19.1 Statistical Methods

19.1.1 Efficacy Analyses

The primary analysis will be the percent change from baseline to last visit in IAD scores. The IAD score at each time point will be estimated using the assessments at each time point. The percent change from baseline will be calculated at the last visit and compared between treatment groups using an analysis of variance with site, treatment, age group (infants vs adults) and interactions as factors in the model. Lack of significance (P<0.05) for the age group-by-treatment will be used as justification for pooling the age groups. If the interaction is significant, the age groups will be analyzed separately. If appropriate, non-parametric procedures (e.g. ranking the data prior to analysis) will be used.

The primary analysis will be done using an intent-to-treat (ITT) population, using all subjects who have at least one dose of their assigned product. For this analysis, dropouts will be considered censored at the time of dropping out. Because two primary endpoints are being tested, Hocherg's procedure will be used to determine statistical significance to preserve the Type I error rate of α =0.05.

A second analysis will be done using a per protocol (PP) set. This analysis will be done on those subjects who were compliant with therapy and completed all procedures. This dataset will be defined prior to database lock, and all reasons for exclusion will be documented.

Analytical methods will be defined in detail in the approved Statistical Analysis Plan (SAP).

Secondary efficacy endpoints in this study will include:

- Time to resolution of severe Category 2 IAD, defined as re-epithelialization of skin. The time to resolution will be tested using a Cox Proportional Hazards model, with treatment group as a fixed factor in the model, and center as a random factor in the model. Other important prognostic factors (e.g., age, type and intensity of incontinence, use of corticosteroids, diabetes, use of warfarin) will be identified and may be included as covariates in the model. Kaplan-Meier estimates of time to re-epithelialization will also be done.

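### The final limit of 0.0483 does not pair with the interim limit of 0.0056: at half information the two give an overall two-sided type I error of 0.0505, and the O'Brien-Fleming variant is not named

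*Combined protocol and SAP*

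**What the plan says.** Section 19.3 of the protocol sets the timing: "one interim analysis will be done after half of the subjects are enrolled". It says that the P-value is "adjusted using an O'Brien-Fleming method" and does not say which version of that method is meant. The interim result "will be considered significant at P <0.0056". For the end of the trial it says: "The result for the analysis after all subjects are complete will be considered significant at P <0.0483".

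Section 19.1.1 gives the error rate to be held, in the sentence on multiplicity: "to preserve the Type I error rate of α =0.05". Section 19.2 states the alternative hypothesis as a difference in either direction, so the test is two-sided. No section gives a spending function, software or other derivation for the two limits.

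**The concern.** A group-sequential pair of limits is chosen jointly. Once the interim limit and its timing are fixed, the target of 0.05 determines the final limit. Here the final limit is looser than the one that belongs with 0.0056 at half information, so the two looks together spend slightly more than 0.05.

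These are the decision thresholds of the primary comparison in a superiority trial. A final P-value just under 0.0483 would be declared significant although the corresponding O'Brien-Fleming limit would not allow it. With the variant unnamed, a reader cannot tell which limit was intended, or how to recompute it if the interim falls early or late.

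**Working it through.** **Inputs.** Overall alpha 0.05 (section 19.1.1); two-sided alternative (section 19.2); one interim at half of the subjects, limits 0.0056 and 0.0483 (section 19.3). The information fraction t = 0.5 is read from the half-enrolment trigger.

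**Formula.** Let Z1 and Z2 be the interim and final test statistics, bivariate normal under the null with correlation √t, and let c1 and c2 be the two-sided critical values. The overall type I error is

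1 − ∫ from −c1 to c1 of φ(x) · [Φ((c2 − √t·x)/√(1−t)) − Φ((−c2 − √t·x)/√(1−t))] dx.

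**1. The stated pair.** P = 0.0056 gives c1 = 2.770, and P = 0.0483 gives c2 = 1.975. With t = 0.5 the integral gives 0.05052. A simulation of 20 million draws gives 0.0505. Moving both limits across their rounding intervals (0.00555 to 0.00565 and 0.04825 to 0.04835) gives 0.0504 to 0.0506, so rounding does not account for the excess.

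**2. Where 0.0056 comes from.** The Lan-DeMets O'Brien-Fleming-type function spends 2 − 2Φ(1.960/√t) by fraction t. At t = 0.5, 1.960/√0.5 = 2.772, and 2 − 2Φ(2.772) = 0.00557, which rounds to the plan's figure. The interim limit is therefore reproduced.

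**3. The final limit that belongs with it.** Holding the interim at 0.0056 and solving for a total of 0.05 gives c2 = 1.9794, or P = 0.04777. The plan's 0.0483 is not reproduced.

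**4. Other variants at two equal looks.** In the classical method c1 = C·√2 and c2 = C. Solving for 0.05 gives C = 1.9774, so c1 = 2.7965.

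| Variant, t = 0.5 | Interim P | Final P |
|---|---|---|
| Stated in section 19.3 | 0.0056 | 0.0483 |
| Lan-DeMets O'Brien-Fleming type, two-sided 0.05 | 0.0056 | 0.0478 |
| Classical O'Brien-Fleming, two-sided 0.05 | 0.0052 (0.00517) | 0.0480 (0.04799) |
| Lan-DeMets as two one-sided 0.025 tests | 0.0031 | 0.0490 |
| Lan-DeMets, one-sided 0.05 | 0.0056 | 0.0482 |

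The last row is nearest to the stated pair but is still not equal to it, and a one-sided test conflicts with the alternative in section 19.2. Read the other way, keeping 0.0483 would require an interim limit of 0.0046.

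**5. Dependence on timing.** Overall two-sided error of the stated pair at other information fractions, which are assumptions because the documents give none beyond one half:

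| t | 0.40 | 0.45 | 0.50 | 0.55 | 0.60 |
|---|---|---|---|---|---|
| Overall error | 0.0512 | 0.0509 | 0.0505 | 0.0502 | 0.0498 |

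The total reaches 0.05 at t = 0.576, about 58%.

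**6. Rounding of the replacement.** With 0.0056 at the interim, a final limit of 0.0478 gives 0.05003 and 0.0477 gives 0.04993. To four decimals, 0.0477 is the largest final limit that does not exceed 0.05.

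**The case against.** The strongest defence is that the plan refers to an O'Brien-Fleming method without restricting it to the classical one. That stands for the interim limit. A reader who knows only the classical constants might infer that 0.0056 is itself an error, or that both limits must become 0.0052 and 0.0480. The documents do not support that, because 0.0056 is exactly what the Lan-DeMets version gives at half information. The defence does not rescue the final limit, since the same version pairs 0.0056 with 0.0478.

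A reader might also add the limits, 0.0056 + 0.0483 = 0.0539, and infer an error rate near 5.4%. That is wrong: the final statistic includes the interim data, the two looks are correlated, and the actual total is 0.0505.

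Timing is a fair further point. The trigger is enrolment, so the information fraction may not be 0.5, and from about 58% the stated pair does hold 0.05. Nothing in the plan points to so late an interim. Subjects may be treated for up to 21 days, so a look taken promptly at half enrolment would tend to have less than half of the last-visit scores, and the excess would then be larger. No accrual figure allows this to be quantified.

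Finally, the size is small, and section 19.1.1 has a larger ambiguity about alpha: it refers to two primary endpoints where only one is defined. Both statements are true. They limit the importance of this point without making the final limit correct.

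**Conclusion.** Wrong as written, with a small effect. At half information the stated limits give an overall two-sided type I error of 0.0505 against 0.05, an excess of about 0.0005. The firm error is the final limit: it should be about 0.0478 if 0.0056 is kept. The decision changes only for a final P-value between about 0.0478 and 0.0483. Under the classical variant the range is 0.0480 to 0.0483, and an interim P-value between 0.0052 and 0.0056 would be affected too.

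The result assumes normal test statistics, a two-sided test, an information fraction of 0.5 and an unchanged sample size. Section 19.3 also lets the interim data drive a re-estimation of the sample size. That could affect the error rate further; it is not included here, and no size is claimed for it.

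**What to change.** Name the O'Brien-Fleming variant in section 19.3 and state a pair of limits that belongs to it. The smallest change is to specify Lan-DeMets O'Brien-Fleming-type spending, keep 0.0056 and replace 0.0483 with 0.0477 (0.04777 rounded down so that the total stays within 0.05). If the sponsor intends the classical method, the pair is 0.0052 and 0.0480; rounded in this way it totals 0.05002, so the unrounded 0.00517 and 0.04799 are better. Add a sentence that the final limit will be recomputed from the information fraction actually reached at the interim if that is not 0.5.

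The cost is one number and one or two sentences, with no change to data collection. The final threshold becomes slightly stricter. With the planning values in section 19.2 (SD 70, difference 45, 51 per group), the standard error is 70·√(2/51) = 13.86 and 45/13.86 = 3.246. Ignoring the interim look and using the normal approximation, power is Φ(3.246 − 1.975) = 0.898 at the stated final limit and Φ(3.246 − 1.980) = 0.897 at 0.0477. The claim of at least 80% power is not affected.

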19.4 Procedures for Accounting for Missing, Unused, and Spurious Data

Subjects who are replaced will not be included in the primary analysis as they will be missing any efficacy data (any IAD assessment). These subjects will be accounted for in the final report. Missing critical efficacy data such as the time to first healing of the IAD or time to significant IAD score reduction will be imputed using last observation carried forward. Also, a sensitivity analysis will be performed on the primary endpoint considering all dropouts in both treatment groups as worsening IAD.

Subject excluded from any subset or per protocol analysis will be documented and justified in the pre-lock meeting minutes.

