6.4 Study Duration

In order to screen, enroll, and complete 102 evaluable subjects, an enrollment period of approximately 18-24 months is anticipated. Each adult subject may be followed for up to a maximum of 42 days or until the subject is discharged. Each pediatric subject may be followed for up to a maximum of 21 days or until the subject is discharged.

- 1. If the subject is discharged prior to 21 days, the subject will still have met the requirements for study completion.
- 2. Adult Subjects (>18years) can remain in the study for up to 21 days following enrollment receiving the Cavilon Advanced Skin Protectant or comparative product. All subjects will be discontinued at this point with the exception of the following 2 scenarios:
 - Subjects randomized to the comparative group, who fail to reach healing at the end of 21-day period with ongoing incontinence may be crossed over to the Cavilon Advanced Skin Protectant group and allowed to continue for up to an additional 21 days.
 - Subjects randomized to the Cavilon Advanced Skin Protectant group, who either re-epithelized or have a positive reduction in their IAD during the 21-day period, but remain hospitalized and continue to have incontinence, may continue to receive the Cavilon Advanced Skin Protectant product for up to an additional 21 days to evaluate prevention of IAD reoccurrence.
 - If a subject completely heals during the study, they may be discontinued at that time.
- 3. Pediatric Subjects Full term (37 weeks) to 18 years) can remain in the study for up to 21 days following enrollment receiving the Cavilon Advanced Skin Protectant product or comparative product. If the subject is discharged prior to 21 days, the subject will still have met the requirements for study completion.
 - Subjects randomized to the comparative group, who fail to improve (IAD) within 3 days of first application in the study may be crossed over to Cavilon Advanced Skin Protectant group and allowed to continue for up to an additional 21 days. The staff should cleanse the skin, complete skin assessments, and photographs prior to application of Cavilon Advanced Skin Protectant.
 - Subjects randomized to Cavilon Advanced Skin Protectant group, who fail to improve (IAD) within 3 days of first application in the study may be discontinued.

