- Pain scores during incontinence management will be measured on a 0-10 scale, and will be analyzed only for those subjects from the ITT dataset who can report pain. This dataset will exclude those who are paraplegic or cannot respond. Infant pain will be measured with the FLACC tool⁴², and adults with the 0-10 Faces tool, and the data will be combined for statistical analysis. For this dataset, the pain scores will be compared by day using an analysis of variance with center, product, age group (infants vs adults), and interactions as factors in the model. If the age group-by-treatment interaction is significant (P<0.05), the data will be analyzed by age group. This response will be considered significant using a Hochberg's procedure for adjusting the P-values for this and the other secondary response of time to re-epithelialization.

- The proportion of subjects on each treatment group with stinging or burning upon application will be compared using a Cochran-Maentel-Haenzel test, stratifying for center.
- Percent change in IAD scores at each visit.
- Efficacy in subjects who switch from the comparative product to the investigational product after failure on the comparative product. For this analysis, the proportion of subjects with resolution of IAD as defined above will be estimated.
- Prevention of IAD in areas that had no denuded skin and remained free of IAD throughout the intervention. This will be estimated and tested using a Cox Proportional hazard model.
- Prevention of IAD, as measured by IAD scores in subjects whose IAD re-epithelialized and who continued on the investigational product. The proportion of subjects who have no progression of IAD, while still experiencing incontinence, will be estimated.
- Patient Quality of Life (QoL) as measured by the EQ-5D-5L questionnaire will be analyzed by comparing the change from baseline in each of the domains. The changes from baseline will be compared using an analysis of variance with center, product, type of skin (denuded or not), and interactions as factors in the model.
- Nursing time will be summarized for a fecal episode occurring post Dose 1 (after first treatment) for a subset of subjects. The nursing times will be summarized for both product groups.
- Incontinence product use will be recorded during the study, and summarized for both product groups. The purpose of this analysis is to provide estimates of total IAD management cost for both regimens.

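### Section 19.4 imputes a missing healing time by LOCF while Section 19.1.1 analyses healing by Cox and Kaplan-Meier; pain, its partner in the Hochberg procedure, has no single defined P-value

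*Combined protocol and SAP*

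**What the plan says.** **Healing.** Section 19.1.1 lists time to re-epithelialization first among the secondary efficacy endpoints. "The time to resolution will be tested using a Cox Proportional Hazards model", with treatment fixed and centre random, and Kaplan-Meier estimates are added. No censoring rule is given there. The section's one censoring statement, "dropouts will be considered censored at the time of dropping out", belongs to the paragraph on the primary intent-to-treat analysis, which is an ANOVA of percent change in IAD score.

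Section 19.4 covers missing critical efficacy data and states that "the time to first healing of the IAD or time to significant IAD score reduction will be imputed using last observation carried forward". It adds that "a sensitivity analysis will be performed on the primary endpoint considering all dropouts in both treatment groups as worsening IAD". Healing has no counterpart to that sensitivity analysis.

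**Exit.** Section 6.4 says: "If the subject is discharged prior to 21 days, the subject will still have met the requirements for study completion". Paediatric subjects on the paste "who fail to improve (IAD) within 3 days of first application in the study may be crossed over", while paediatric non-improvers on Cavilon may be discontinued. Section 12 keeps data up to a serious pressure ulcer or to the need for topical treatment. It does not address discharge.

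**Pain.** In Section 19.1.1, "the pain scores will be compared by day using an analysis of variance with center, product, age group (infants vs adults), and interactions" as model factors. Hochberg's procedure is then named "for adjusting the P-values for this and the other secondary response of time to re-epithelialization".

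**The concern.** An event that has not happened has no value to carry forward. In a Cox or Kaplan-Meier analysis, a subject who leaves unhealed contributes time at risk up to the last assessment and is then censored. Section 19.4 names a different rule for this endpoint. The sentence that would supply censoring is attached to an ANOVA of a continuous score, where it has no function. The plan also does not say whether an unhealed subject discharged before Day 21, who counts as a completer, has a missing healing time.

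Pain has a smaller gap. A by-day ANOVA has no day factor and gives one P-value per assessment day, yet pain takes one place in a two-member Hochberg procedure. The reading is not settled either: Sections 10, 11.1 and 11.2 and the Synopsis variously place it before, during or after cleansing, and before or after application.

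Healing and pain are the only two secondary responses with stated multiplicity control, so each needs one uniquely defined P-value.

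**Working it through.** **The plan's own figure.** Section 19.2 gives 51 per group, SD 70 and difference 45, with at least 80% power. Check: 45 / (70 × √(2/51)) = 3.246; 3.246 − 1.960 = 1.286; power 90%. The statement is true as a floor, but it concerns the primary endpoint. No power or event rate is stated for healing or pain, so what follows is illustrative.

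**Four readings of LOCF for healing**
1. Fill only missed assessments: harmless.
2. Keep the last observed time with status unhealed: identical to censoring.
3. Treat the last observed time as the healing time: exit becomes an event.
4. Carry unhealed status to Day 21: the subject stays at risk after leaving.

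**Closed-form check of readings 3 and 4** (assumed median healing 14 days, 20% lost by Day 21, continuous time).
- Rates: λ = ln 2 / 14 = 0.0495; μ = −ln(0.8) / 21 = 0.0106.
- True healing by Day 21, recovered by censoring: 1 − e^(−21λ) = 64.6%.
- Reading 3: 1 − e^(−21(λ+μ)) = 71.7%.
- Reading 4: λ/(λ+μ) × 71.7% = 59.0%.

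**Power simulation.** From the documents: 51 per arm and the schedule's assessment days 3, 5, 8, 10, 12, 15, 17, 19 and 22. Assumed: exponential healing at 0.10 versus 0.05 per day (hazard ratio 2.0), equal exponential exit, log-rank test. Subjects leaving before Day 3 are replaced, to reflect Sections 6.3 and 12; Day 3 as the cut-off is an assumption.

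| Exit per day | Censored | Exit counted as healing | Unhealed carried to end |
|---|---|---|---|
| 0.01 | 84% | 79% | 80% |
| 0.03 | 80% | 66% | 72% |
| 0.05 | 75% | 52% | 65% |

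Simulation error is about one to two points. Without replacement, the last row is 69/40/50%. Under reading 1, with 10–20% of assessments missed and no replacement, power is within 0.4 points of censoring.

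**Type I error** (healing 0.06 per day in both arms). With equal exit it is about 5% under every rule. With exit 0.05 versus 0.03 it is 5% with censoring, about 15% if exit counts as healing, and about 9% if unhealed is carried forward.

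**Pain.** The schedule has nine skin-assessment days after Day 1, ten with Day 1. Two-member Hochberg at 0.05 rejects something if the smaller P ≤ 0.025 or both P ≤ 0.05. As a worst case, let the smallest daily P stand for pain. With nine independent days and an independent healing P:
- P(pain ≤ 0.025) = 1 − 0.975⁹ = 0.204; P(pain ≤ 0.05) = 1 − 0.95⁹ = 0.370.
- Familywise error = 0.204 + 0.025 − 0.204 × 0.025 + (0.370 − 0.204) × 0.025 = 0.228.

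Days within a subject are correlated. By simulation, nine days at correlation 0.3/0.5/0.7/0.9 give 0.205/0.174/0.138/0.091, and ten days give 0.220/0.184/0.144/0.094. One pre-named contrast gives 0.050.

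**The case against.** Several points on the other side stand.

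- Two of the four LOCF readings do no harm. A reader might infer that the plan counts exit as healing; it never says so.
- Section 12 truncates data at some exits. With the misplaced censoring sentence, this suggests that censoring was intended. But Section 12 does not cover discharge, and if the sentence in 19.1.1 is read as applying to healing, it contradicts 19.4.
- The replacement rules remove the earliest leavers and shrink the loss. The table allows for this.
- A reader might infer inflated type I error for healing. With equal exit there is none, and the documents give no exit rates by arm; 0.05 versus 0.03 is only an assumption.
- A reader might infer that pain error control fails at 20% or so. That needs the smallest daily P-value to be chosen, which the plan does not say; it treats pain as one response.
- Section 19.1.1 defers detail to a SAP, and no separate SAP text is in the document provided. A SAP could close the pain gap. It is a weaker answer for healing, because 19.4 already states the rule, and under 19.5 a SAP that censored instead would be a deviation to justify.

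**Conclusion.** The healing rule is wrong as written. Sections 19.1.1 and 19.4 do not fit together, and the stated rule admits readings that bias the result. Under the assumed rates, the harmful readings cost about 4–5 points of power at exit 0.01 per day, 8–14 at 0.03 and 10–23 at 0.05. Type I error rises, to about 15% or 9% in the example, only if exit differs by arm. The documents do not support a claim that bias will occur, only that the text permits it.

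The pain gap is real but secondary: no single P-value is defined for its place in the Hochberg procedure. The 9–22% familywise error (between-day correlation 0.9 to 0.3) is a worst case, not a property of the plan. Both matters concern secondary endpoints and should be corrected. Neither affects the primary percent-change comparison.

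**What to change.** **Healing**
- In 19.4, restrict LOCF to the IAD score used for percent change at the last visit, remove the two time-to-event examples, and state that LOCF does not apply to time-to-event endpoints.
- In 19.1.1, move the censoring sentence from the primary ANOVA to the Cox and Kaplan-Meier analysis.
- Censor unhealed subjects at their last IAD assessment on randomized product, including those discharged early and those covered by Section 12.
- Paediatric crossover or discontinuation follows failure to improve, so censoring there is informative. Add one sensitivity analysis that keeps these subjects as unhealed to Day 21.

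**Pain**
- Name one reading and reconcile the Synopsis and Sections 10, 11.1 (cleansing and both product-application parts) and 11.2 with it.
- Name one contrast over the 21-day randomized period, either one pre-named day or an average over days, as the single Hochberg P-value.
- Report by-day and by-age-group results as descriptive.

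**Cost.** Wording changes and one sensitivity analysis; no new visits or subjects. For pain scores already collected under Section 11.1, the timing must be checked on the CRF. By-day and by-age-group pain results can no longer support a stand-alone claim.
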